10.4.3 Secondary Endpoint(s)

Table 10.4.3-1: Secondary Endpoints

Secondary Endpoint	Description	Timeframe
ORR is defined as the proportion of participants with a confirmed BOR of CR or PR by RECIST v1.1.	The ORR and its corresponding 95% exact CI will be calculated by Clopper-Pearson method for each arm, based on BICR and on investigator by RECIST v1.1. The ORR difference will also be estimated by 95% CI and in each subgroup.	Time from randomization and every 6 weeks after randomization for the first 48 weeks, then every 12 weeks, until progression, death, study discontinuation or initiation of subsequent therapy
DOR is defined for participants who have a confirmed CR or PR as the date from first documented CR or PR per RECIST v1.1 to the date of the documentation of disease progression or death due to any cause, whichever is earlier.	The median DOR will be estimated using the Kaplan-Meier method with corresponding 95% CI.	From the time of first documentation of objective response, until progression, death, study discontinuation or initiation of subsequent therapy

Table 10.4.3-1: Secondary Endpoints

Secondary Endpoint	Description	Timeframe
PFS is defined for all randomized participants as the date from randomization to the date of the documentation of disease progression by BICR or death due to any cause, whichever is earlier.	
The PFS curve will be estimated using the Kaplan-Meier product-limit method. If testing occurs, a log-rank test stratified by the PD-L1 expression (< 1%, 1% - 49%, ≥ 50%) and histology will be used to compare PFS based on RECIST v1.1 by BICR between the 2 treatment arms in the all randomized population. The HR and corresponding 2-sided 95% CI in these populations will be estimated using a Cox proportional hazard model, with treatment arm as a single covariate, stratified by PD-L1 expression and histology.
 
PFS in each treatment arm will be estimated in the PD-L1 defined subgroups.
	Time from randomization and every 6 weeks after randomization for the first 48 weeks, then every 12 weeks, until progression (by BICR), death, study discontinuation or initiation of subsequent therapy
OS is defined as the time from randomization to the time of death due to any cause	
The OS curve will be estimated using the Kaplan-Meier techniques in the PD-L1 ≥ 1% and all randomized populations. A 2-sided 95% CI for median OS in each treatment arm will be computed via the log-log transformation method. If testing occurs, a log-rank test stratified by the PD-L1 expression (< 1%, 1% - 49%, ≥ 50%) and histology will be used to compare OS between the 2 treatment arms. The HR and corresponding 2-sided 95% CI for OS in these populations will be estimated using a Cox proportional hazards model, with treatment arm as a single covariate, stratified by PD-L1 expression and histology.
	Time from randomization until death for any cause
The incidence of AEs, SAEs, TRAEs, AEs leading to discontinuation, and deaths in the randomized population	
Descriptive statistics of AEs will be presented using NCI CTCAE v5. On-study incidence of AEs, SAEs, and TRAEs, and AEs leading to discontinuation will be tabulated using worst grade per NCI CTCAE v5 criteria by System Organ Class and Preferred Term.
	Time from first dose, up to 100 days after the last treatment of study drug

Abbreviations: AE, adverse event; BICR, blinded independent central review; BOR, best overall response; CI, confidence interval; CR, complete response; DOR, duration of response; HR, hazard ratio; NCI CTCAE, National Cancer Institute Common Terminology Criteria for Adverse Events; ORR, objective response rate; OS, overall survival; PD-L1, programmed death-ligand 1; PFS, progression-free survival; PR, partial response; RECIST, Response Evaluation Criteria in Solid Tumors; SAE, severe adverse event; TRAE, treatment-related adverse event.

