4 OBJECTIVES AND ENDPOINTS

Table 4-1: Objectives and Endpoints

Objectives	Endpoints
Primary	

 To compare the PFS of BMS-986207 in combination with nivolumab plus ipilimumab (Arm A) versus nivolumab plus ipilimumab (Arm B) in participants with 1L Stage IV NSCLC expressing PD-L1 \geq 1% 	
 PFS in participants with tumors expressing PD-L1 \geq 1% based on RECIST v1.1 by BICR
Secondary	

 To compare the PFS of BMS-986207 in combination with nivolumab plus ipilimumab (Arm A) versus nivolumab plus ipilimumab (Arm B) in all randomized participants with 1L Stage IV NSCLC 	
 PFS in all randomized participants based on RECIST v1.1 by BICR

 To assess the safety and tolerability of BMS-986207 in combination with nivolumab plus ipilimumab (Arm A) and nivolumab plus ipilimumab (Arm B) in participants with 1L Stage IV NSCLC 	
 Incidence of AEs, SAEs, AEs leading to discontinuation, and deaths

 To estimate the ORR of BMS-986207 in combination with nivolumab plus ipilimumab (Arm A) and nivolumab plus ipilimumab (Arm B) in all randomized participants with 1L Stage IV NSCLC and in subgroups defined by PD-L1 expression 	
 ORR in all randomized participants and in subgroups defined by PD-L1 expression (PD-L1 \geq 1% , < 1%, 1% - 49%, and \geq 50%) based on RECIST v1.1 by BICR assessment

Table 4-1: Objectives and Endpoints

Objectives	Endpoints

 To compare OS of BMS-986207 in combination with nivolumab plus ipilimumab (Arm A) versus nivolumab plus ipilimumab (Arm B) in randomized participants with tumors expressing PD-L1 $\geq 1\%$ 	
 OS in participants with tumors expressing PD-L1 $\geq 1\%$

 To compare OS of BMS-986207 in combination with nivolumab plus ipilimumab (Arm A) versus nivolumab plus ipilimumab (Arm B) in all randomized participants with 1L Stage IV NSCLC 	
 OS in all randomized participants

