9.2.1 Time Period and Frequency for Collecting AE and SAE Information

All SAEs must be collected from the time of signing the consent, including those thought to be associated with protocol-specified procedures, and within 100 days following discontinuation of dosing. For participants randomized to treatment and never treated with study drug, collect SAEs for 30 days from the date of randomization.

Collect all nonserious AEs (not only those deemed to be treatment-related) continuously during the treatment period and for a minimum of 100 days following discontinuation of study intervention. The collection of non-serious AEs (with the exception of non-serious AEs related to SARS-CoV-2 infection) should begin at initiation of study intervention.

The investigator must report any SAE that occurs after these time periods and that is believed to be related to study intervention or protocol-specified procedure (eg, a follow-up skin biopsy, tissue biopsy).

- Medical occurrences that begin before the start of study intervention but after obtaining informed consent will be recorded on the appropriate section of the CRF module.
- All SAEs will be recorded and reported to Sponsor or designee within 24 hours, as indicated in Appendix 3.

- The investigator will submit any updated SAE data to the Sponsor or designee within 24 hours of updated information being available.
- All SAEs, and all AEs (SAEs and non-serious AEs) associated with confirmed or suspected SARS-CoV-2 infection must be collected from the date of the participant's written consent until 100 days following discontinuation of dosing.

Investigators are not obligated to actively seek AEs or SAEs in former study participants. However, if the investigator learns of any SAE, including a death, at any time after a participant has been discharged from the study, and he/she considers the event reasonably related to the study intervention or study participation, the investigator must promptly notify the Sponsor.

The method of evaluating and assessing causality of AEs and SAEs and the procedures for completing and reporting/transmitting SAE reports are provided in [Appendix 3](#).

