10.3 Analysis Sets

For the purposes of analysis, the following populations are defined:

Population	Description
Enrolled	All participants who sign informed consent and are registered in IRT
Treated	All participants who received any amount of study intervention
Randomized	All participants who were randomized using IRT
Randomized PD-L1 \geq 1%	All participants who were randomized using IRT with \geq 1% PD-L1 tumor expression
Safety-evaluable	All randomized participants who have received study intervention (all 3 components) and have completed the safety-evaluation period of 12 weeks, or who discontinued any study intervention due to toxicity prior to completing the safety-evaluation period.
PK	All participants who received at least 1 dose of study intervention and had any available concentration-time data
Immunogenicity	All treated participants who have baseline and at least 1 post-baseline pre-infusion immunogenicity assessment

Abbreviations: IRT, interactive response technology; PD-L1, programmed death-ligand 1; PK, pharmacokinetic.

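### The AE row names the randomized population although its window starts at first dose, and its only by-arm summary is crude incidence that depends on how long each arm is treated

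*Combined protocol and SAP*

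**What the plan says.** The AE row of Table 10.4.3-1 (Section 10.4.3) gives the endpoint as "The incidence of AEs, SAEs, TRAEs, AEs leading to discontinuation, and deaths in the randomized population" and its timeframe as "Time from first dose, up to 100 days after the last treatment of study drug". On method, "Descriptive statistics of AEs will be presented using NCI CTCAE v5", and on-study incidence including "AEs leading to discontinuation will be tabulated using worst grade per NCI CTCAE v5 criteria by System Organ Class and Preferred Term". The row names no exposure-adjusted rate, fixed-time incidence or time-to-event analysis of AEs, and neither does the rest of the protocol.

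Section 10.3 defines the Randomized set as "All participants who were randomized using IRT" and the Treated set as "All participants who received any amount of study intervention". No safety analysis in the document is assigned to the Treated set.

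Section 9.2.1 sets collection: "For participants randomized to treatment and never treated with study drug, collect SAEs for 30 days from the date of randomization". It starts collection of non-serious AEs at the first study intervention, with an exception for events related to SARS-CoV-2.

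Section 10.5.1 uses a fixed 12-week period, but only for the Arm A boundary on Grade 3 to 4 treatment-related AEs (TRAEs). Section 10.4 leaves the selection of participants for analysis to a SAP that is not part of the document under review.

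**The concern.** There are two separate points in one table row.

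The first is the denominator. A participant who was never dosed has no first dose from which to start the window, cannot have a TRAE, has no routine non-serious AE collection, and has SAEs collected for only 30 days. Counting such participants lowers every incidence.

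The second is the length of observation. Each participant is observed for their own treatment time plus 100 days, and treatment normally runs to progression, up to two years. If BMS-986207 delays progression as the design assumes, Arm A is dosed and observed for longer. A crude proportion can then be higher in Arm A even when the monthly risk is the same in both arms.

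Safety of the triplet is a secondary objective covering both arms, and the by-arm tables will be read side by side when benefit and risk are weighed.

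**Working it through.** The AE row states no figure to reproduce, so the check asks how far crude incidence moves under stated assumptions.

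**Inputs from the protocol.** Arm B median PFS 5 months and HR 0.605 (Section 10.2, for PD-L1 ≥ 1%, applied here to everyone). Treatment capped at 24 months (Section 5.1.2). AE window continuing 100 days after last treatment (Table 10.4.3-1). Reference Grade 3 to 4 TRAE rate 32.8% and TRAE discontinuation rate 18.1% with nivolumab plus ipilimumab (Section 3.3.3). About 180 participants at 2:1, so 120 and 60.

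**Assumptions.** Treatment ends at progression. PFS is exponential. The AE hazard h is the same in both arms.

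**Denominator.** If a fraction f is never dosed, an incidence p reads p(1 − f). For p = 32.8%:
- f = 1%: 32.5%
- f = 2%: 32.1%
- f = 5%: 31.2%

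The protocol gives no value for f. Section 7.1 asks for dosing within 3 calendar days of randomization, which suggests that f is small.

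**Treatment time.** The PFS hazards are λ_B = ln 2/5 = 0.1386 and λ_A = 0.605 × 0.1386 = 0.0839 per month, so the Arm A median is 5/0.605 = 8.26 months. Mean treatment time is (1 − e^(−24λ))/λ, which gives 10.3 months in Arm A and 7.0 in Arm B. With the tail w = 100 days = 3.29 months, mean observation time is 13.6 and 10.2 months.

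**Crude incidence with constant risk.** P = 1 − e^(−hw) × [λ/(λ+h) × (1 − e^(−24(λ+h))) + e^(−24(λ+h))].
- Setting P = 32.8% in Arm B gives h = 0.0419 per month and e^(−hw) = 0.8715.
- Arm B check: 1 − 0.8715 × (0.7680 × 0.9869 + 0.0131) = 32.8%.
- Arm A: 1 − 0.8715 × (0.6670 × 0.9511 + 0.0489) = 40.4%.

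**Crude incidence with risk confined to the first K months.** Exposure becomes min(T + w, K), where T is treatment time, and h is re-solved for 32.8% in Arm B.

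| Duration of risk (assumed) | h per month | Arm B | Arm A | Gap, points |
|---|---|---|---|---|
| 3 months | 0.1325 | 32.8% | 32.8% | 0 |
| 6 months | 0.0720 | 32.8% | 33.6% | 0.8 |
| 12 months | 0.0491 | 32.8% | 36.4% | 3.6 |
| Constant | 0.0419 | 32.8% | 40.4% | 7.6 |

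The 3-month gap is zero because the 100-day tail alone (3.29 months) covers the whole risk period for every dosed participant who stays in follow-up.

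Adding equal stopping for other reasons (18.1%, assumed to accrue over 6 months, so ln(1/0.819)/6 = 0.033 per month) reduces the constant-risk gap to 5.8 points.

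**Scale.** The standard error of a 120 versus 60 difference at 32.8% is √(0.328 × 0.672 × (1/120 + 1/60)) = 7.4 points.

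**What removes the artefact.** With constant h = 0.0419, incidence within 12 weeks (2.76 months) of first dose is 1 − e^(−0.0419 × 2.76) = 10.9% in both arms, and the person-time rate ratio is 1.0. Cumulative incidence with end of treatment as a competing event does not remove it. At 12 months, h/(h+λ) × (1 − e^(−12(h+λ))) with h = 0.042 gives 26.0% in Arm A and 20.6% in Arm B.

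**The case against.** The strongest reply is that this is a descriptive table. The PFS and OS objectives say compare, while the safety objective says assess. No safety test or difference is planned. A reader might infer that the plan contains a biased formal safety comparison, and the documents do not support that. What stands is narrower: by-arm crude tables are the only planned summary, and they will be compared informally.

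A reader might also infer that longer treatment in Arm A must look like toxicity. That needs Arm A to be treated longer and risk to persist, and it vanishes for early-onset events. Treatment beyond progression is allowed (Section 8.1.2), so PFS is only a proxy for exposure. If risk exists only while on drug, extra events in a longer-treated arm are a real consequence of the regimen. A calculation that stops observation at progression gives Arm A 35.4% to 44.9% against 33% in Arm B, a gap of 2 to 12 points. It omits the 100-day tail and the two-year cap, so it does not describe the planned window.

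If Arm A stopped early for toxicity, the crude gap could shrink or reverse. That would not be wholly hidden, because AEs leading to discontinuation are tabulated and collection continues for 100 days.

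Other parts of the plan help. Section 10.5.1 monitors Arm A over 12 weeks and the DMC sees unblinded safety data (Section 10.5.1.2). Neither supplies a fixed-window by-arm summary for the final analysis.

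On the population, Section 10.4 defers participant selection to the SAP, and the row's own timeframe points to dosed participants. This is fairly called an inconsistency with a small effect. It still needs correcting, because the protocol names the wrong set.

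**Conclusion.** The concern holds in a limited form. The AE row contradicts itself: its population includes people for whom its window never starts. The effect is a reduction of 0.3 to 1.6 points on 32.8% if 1% to 5% are never dosed (assumed), in the opposite direction to the exposure effect expected under the design.

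The crude summary also depends on treatment duration. Under the design assumption the artefact is 0 to about 8 points against Arm A, at most about one standard error, and it could reverse if Arm A stops earlier. The size rests on PFS standing in for treatment time, on HR 0.605 applying to all participants, on an equal hazard in both arms, and on an assumed duration of risk. It does not show that the safety analysis will mislead; it shows that the planned table alone cannot separate longer exposure from greater toxicity.

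**What to change.** In the AE row of Table 10.4.3-1, replace the randomized population with the Treated set. Deaths among never-dosed participants remain covered by the OS analysis.

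Keep the crude table. Beside it, report by arm:
- the incidence of Grade 3 to 4 TRAEs, SAEs and AEs leading to discontinuation within 12 weeks of first dose, counting events whether or not treatment has ended. The 100-day collection covers this 84-day window for every dosed participant apart from death or withdrawal;
- rates of the same events per 100 person-months over the AE window.

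Report both. If risk is concentrated early, later person-months dilute the rate in the longer-treated arm, and the 12-week table guards against that.

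Do not make cumulative incidence with end of treatment as a competing event the between-arm comparison, because it still depends on treatment duration.

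The cost is one wording change and a few extra tables from data already collected.

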10.4.4 Exploratory Endpoint(s)

Table 10.4.4-1: Exploratory Endpoints

Exploratory Endpoint	Description	Timeframe
Pharmacokinetics		
Ctrough and Ceoi	Summary statistics to assess attainment of steady state: geometric means and coefficients of variation, by treatment and by day, Ctrough plots versus time	Time from first study intervention up to last treatment of study drug or discontinuation, or Cycle 17, whichever occur first.
Immunogenicity		

Incidence of ADA to BMS-986207, nivolumab, and ipilimumab
 
Baseline ADA-positive participant is defined as a participant who has an ADA-detected sample at baseline
 
ADA-positive participant is a participant with at least 1 ADA-positive sample relative to baseline after initiation of the treatment
 
Summary measures of ADA titers and kinetics (onset and duration)
 
Assessments of ADA effect on efficacy, safety, and PK
	
Frequency distribution of baseline ADA-positive participants and ADA-positive participants after initiation of the treatment for each of BMS-986207, nivolumab, and ipilimumab.
 
Summary statistics/plots of ADA titers.
 
Table of ADA onset and duration.
 
Summary table/plot of ORR and occurrence of select AEs by ADA status.
 
Plots of PK parameters/exposures by ADA status may be generated as part of a population PK analysis and reported separately.
	Time from first study intervention up to last treatment of study drug or discontinuation, or Cycle 17, whichever occur first.
Biomarker Analysis		
Summary measures of change (or % change) from baseline in various biomarkers in the tumor and peripheral blood	Summary statistics/plots by planned study day and dose in each arm. Plots of the time course of biomarkers by treatment arm	Time from first study intervention up to last treatment of study drug or discontinuation, or Cycle 17, whichever occur first.
Clinical Outcomes Assessments Analysis		
NSCLC-SAQ total score based on the PGIS and PGIC as anchor measures	Summary statistics of change in NSCLC-SAQ total score based on the PGIS and PGIC as anchor measures tabulated by treatment arm and time points	Time from randomization until death, loss to follow-up, withdrawal of consent, or conclusion of the study, whichever comes first, for a period of up to 4 years from randomization.

Table 10.4.4-1: Exploratory Endpoints

Exploratory Endpoint	Description	Timeframe
NSCLC-SAQ total score and FACT-G7	Mean change from baseline in NSCLC-SAQ total score and FACT-G7 by treatment arm	Time from randomization until death, loss to follow-up, withdrawal of consent, or conclusion of the study, whichever comes first, for a period of up to 4 years from randomization.
EQ-5D-5L utility index and EQ VAS scores	Mean change from baseline in EQ-5D-5L utility index and EQ VAS scores by treatment arm	Time from randomization until death, loss to follow-up, withdrawal of consent, or conclusion of the study, whichever comes first, for a period of up to 4 years from randomization.

Abbreviations: ADA, anti-drug antibody; AE, adverse event; Ceoi, end of infusion concentration; Ctrough, observed serum trough concentration; EQ VAS, EuroQol visual analog scale; FACT-G7, Functional Assessment of Cancer Therapy - General - 7 item version; NSCLC-SAQ, Non Small Cell Lung Cancer Symptom Assessment Questionnaire; ORR, objective response rate; PGIC, Patient Global Impression of Change; PGIS, Patient Global Impression of Severity; PK, pharmacokinetic.

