5.1.2 Treatment Period

Treatment arms are illustrated in [Figure 5.1-1](#).

The randomized treatment period will assess efficacy and safety of BMS-986207 in combination with nivolumab plus ipilimumab (Arm A) versus nivolumab plus ipilimumab (Arm B).

After central laboratory confirmation of PD-L1 expression, approximately 180 participants (see [Section 10.2](#)) will be stratified by PD-L1 expression (< 1%, 1% - 49%, or ≥ 50%) and tumor histology (squamous versus nonsquamous) and randomized in a 2:1 ratio to:

- **Arm A:** Nivolumab 360 mg Q3W + ipilimumab 1 mg/kg Q6W + BMS-986207 600 mg Q3W
- **Arm B:** Nivolumab 360 mg Q3W + ipilimumab 1 mg/kg Q6W + placebo Q3W

Participants, investigators, and site staff will be blinded (single-blind) to treatment assignment. The DMC and Sponsor will be unblinded to treatment assignment for the purpose of safety evaluation. Treatment information access will not be used by the Sponsor to perform by-arm efficacy analyses. See [Section 5.1.4](#) for further information regarding the DMC and [Section 7.3](#) for further information regarding blinding. Additional information regarding blinding will also be provided in the statistical analysis plan (SAP).

All participants will be treated for up to 2 calendar years from start of study intervention regardless of treatment delays (up to 18 cycles, 42 days/cycle), until progression, unacceptable toxicity, death, or withdrawal of consent, whichever occurs first. Continuous safety evaluation and tumor assessment will guide the decision to treat a participant with additional cycles of study intervention if the participant has confirmed clinical benefit (up to a maximum of 2 years).

Dose reductions of study interventions are not permitted. Separate assessments of study interventions will be used in considering criteria for dose delay, resumption, and discontinuation (see [Sections 7.4.1](#), [7.4.2](#), and [8.1.1](#)).

Physical examinations, vital sign measurements, 12-lead ECG, and clinical laboratory evaluations will be performed at selected times throughout the dosing interval (see [Section 2](#)). Participants will be closely monitored for AEs throughout the study. Samples will be collected before and after study drug administration for PK analysis and pharmacodynamic parameter measurements (see [Section 9.5](#) for further details).

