9.5 Pharmacokinetics and Immunogenicity Assessments

Samples for PK and immunogenicity assessments for BMS-986207, nivolumab, and ipilimumab will be collected for participants at the time points indicated in [Table 9.5-1](#). All on-treatment PK and immunogenicity time points are intended to align with days on which study intervention is administered. If it is known that a dose is going to be delayed, then collect the predose sample just prior to the delayed dose. However, if a predose sample is collected, but the dose is subsequently delayed, do not collect an additional predose sample.

Draw blood samples from a site other than the infusion site (ie, contralateral arm) on days of infusion for all pre-dose and end of infusion-PK (EOI-PK) samples. Please ensure accurate documentation of the time and date of sample collection. If the infusion was interrupted, the interruption details will also be documented on the CRF.

End of infusion (EOI) samples for nivolumab, ipilimumab and BMS-986207 should be collected immediately following the last drug infusion (preferably within 5 minutes after end of infusion) on the contralateral arm (ie, the arm not for the infusion). Since the EOI-PK sample is drawn with the intent of accurately estimating the maximum concentration of the drug, draw the EOI-PK when all the study drug has been infused. If the site infuses drug without a flush, then collect the EOI-PK sample within approximately 5 minutes after end of infusion. If a flush is administered to clear the IV lines of the drug and to ensure delivery of the entire drug dose, then draw the EOI-PK sample within approximately 5 minutes after end of the flush. If the end of infusion is delayed to beyond the nominal infusion duration, the collection of this sample should also be delayed accordingly.

Ctrough and EOI concentrations (Ceoi) of BMS-986207, nivolumab and ipilimumab will be reported. In addition, concentration-time data may be used in an integrated population PK analysis along with data from other studies, which will be the subject of a separate report.

Concentration and ADA analyses for each study drug will be performed by validated bioanalytical method(s). Immunogenicity samples positive for anti-nivolumab, anti-ipilimumab, and anti-BMS-986253 may be analyzed for neutralizing antibodies by validated methods.

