Bioanalytical samples designated for assessments (eg, immunogenicity, PK, or biomarker) from the same collection time point may be used interchangeably for analyses, if required (including, but not limited to, insufficient volume for complement assessment, to follow-up on suspected immunogenicity related AE, etc).

Additionally, residual bioanalytical samples will be archived and may be used for potential exploratory bioanalysis (including, but not limited to, analysis of drug-ADA immune complexes, metabolite analyses, etc) and or for additional method purposes (including, but not limited to, cross-validation, ADA/PK selectivity, cutpoint, etc).

Treatment assignments will be released to the bioanalytical laboratory in order to minimize unnecessary analysis and/or reanalysis of PK/ADA samples. Placebo samples will not be analyzed.

Further details of sample collection, processing, and shipment will be provided in the laboratory/procedure manual.

Table 9.5-1: Pharmacokinetic and Immunogenicity Sampling Schedule for BMS-986207, Nivolumab, and Ipilimumab

Study Day of Sample Collection (1 Cycle = 6 weeks)	Event	Time Relative to Nivolumab Dose (hr:min)	BMS-986207 PK Serum Sample	Nivolumab PK Serum Sample	Ipilimumab PK Serum Sample	BMS-986207 IMG (ADA) Serum Sample	Nivolumab IMG (ADA) Serum Sample	Ipilimumab IMG (ADA) Serum Sample
Cycle 1 Day 1	Predose ^a	00:00	X	X	X	X	X	X
	End of infusion ^b	See note ^b	X	X	X			
Cycle 1 Day 8		168:00	X	X	X			
Cycle 1 Day 15		336:00	X	X	X			
Cycle 1 Day 22	Predose ^a	00:00	X	X	X	X	X	
Cycle 1 Day 29 ^c		168:00	X	X	X			
Cycle 2 Day 1	Predose ^a	00:00	X	X	X	X	X	X
Cycle 2 Day 22	Predose ^a	00:00	X	X	X			
Cycle 3 Day 1	Predose ^a	00:00	X	X	X	X	X	X
	End of infusion ^b	00:00	X	X	X			
Cycle 4 Day 1	Predose ^a	00:00	X	X	X	X	X	X
Every 4 cycles starting at Cycle 5 Day 1 until Cycle 17 (C5D1, C9D1, C13D1, C17D1)	Predose ^a	00:00	X	X	X	X	X	X

Abbreviations ADA, anti-drug antibody; C, cycle; Cmax, maximum concentration; D, day; EOI, end of infusion; IMG, immunogenicity; IV, intravenous; PK, pharmacokinetic.

- ^a All predose samples for nivolumab, ipilimumab and BMS-986207 should be taken prior to the start of nivolumab infusion. If it is known that a dose is going to be delayed, then collect the predose sample just prior to the delayed dose. However, if a predose sample is collected, but the dose is subsequently delayed, do not collect an additional predose sample.

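### Comparing ORR by ever-positive ADA status is biased because ADA sampling stops with treatment, so responders give more samples; add a Week 6 landmark comparison and label the planned table as association

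*Combined protocol and SAP*

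**What the plan says.** Section 10.4.4, Table 10.4.4-1, sets the definition: "ADA-positive participant is a participant with at least 1 ADA-positive sample relative to baseline after initiation of the treatment". It has no fixed window and takes no account of how many samples a participant gave. The planned output is "Summary table/plot of ORR and occurrence of select AEs by ADA status". It serves an endpoint worded as "Assessments of ADA effect on efficacy, safety, and PK", which also appears in Table 4-1. The timeframe is "Time from first study intervention up to last treatment of study drug or discontinuation, or Cycle 17, whichever occur first".

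Section 9.5 ties sampling to dosing: "All on-treatment PK and immunogenicity time points are intended to align with days on which study intervention is administered". Table 9.5-1 schedules ADA samples for BMS-986207 and nivolumab at baseline, C1D22, C2D1, C3D1 and C4D1, then "Every 4 cycles starting at Cycle 5 Day 1 until Cycle 17". With 6-week cycles, the post-baseline samples fall at Weeks 3, 6, 12, 18, 24, 48, 72 and 96, so eight at most. Ipilimumab has no C1D22 ADA sample, so seven at most. The table has no follow-up row.

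Under Section 5.1.2, treatment runs "until progression, unacceptable toxicity, death, or withdrawal of consent, whichever occurs first", within a two-year limit and with some treatment beyond progression allowed. The Immunogenicity population (Section 10.3) needs a baseline and only one post-baseline sample. No landmark, time-dependent status or adjustment for number of samples appears. Section 10.4.5 defers exploratory PK and biomarker analyses to the SAP and does not name immunogenicity.

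**The concern.** The grouping variable is built from data collected after treatment starts, and how much is collected depends on the outcome being compared. A participant who progresses early leaves sampling after two or three post-baseline samples. A responder can give six to eight. Even if ADA has nothing to do with response, the ever-positive group will contain too many responders.

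The direction matters. An assessment of ADA against efficacy is there mainly to detect a loss of efficacy in participants who develop antibodies. A bias that raises ORR in ADA-positive participants works against finding it. The same dependence on time on treatment also confounds the AE comparison, though not in a predictable direction.

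**Working it through.** The protocol gives no design figure for this analysis, so there is none to reproduce. The check asks how large the ORR difference would be if ADA were unrelated to response.

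**Inputs from the protocol.** Table 5.4.2-1, nivolumab plus ipilimumab, PD-L1 ≥ 1%: ORR 142/396 = 35.9%, median PFS 5.06 months, median DOR 23.16 months. Section 5.4.4: median time to response 2 to 4 months (2.5 used). Section 3.3.3: 18.1% discontinued for a TRAE. Section 3.2.2.3: 2 of 63 ADA-positive for BMS-986207.

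**Assumptions.** Responders stay on treatment for 2.5 months plus an exponential time with median 23.16 months. Non-responders are exponential, calibrated to the overall median PFS. Overall ADA incidence is 5 to 20%, because the protocol gives no rate for nivolumab or ipilimumab.

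**Calibration.** Responders progression-free at 5.06 months: 2^(−2.56/23.16) = 0.926. Non-responders must then satisfy 0.359 × 0.926 + 0.641 × S = 0.5, so S = 0.26. Their median is 5.06 × ln 2 / (−ln 0.26) ≈ 2.6 months.

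**Fraction still on treatment at each ADA visit** (4.35 weeks per month):

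| Week | 3 | 6 | 12 | 18 | 24 | 48 | 72 | 96 |
|---|---|---|---|---|---|---|---|---|
| Responders | 1.00 | 1.00 | 0.99 | 0.95 | 0.91 | 0.77 | 0.66 | 0.56 |
| Non-responders | 0.83 | 0.69 | 0.48 | 0.33 | 0.23 | 0.05 | 0.01 | 0.00 |

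Each row sums to the mean number of samples: 6.8 and 2.6. The 17% of non-responders with no post-baseline sample are outside the Immunogenicity population. Among those inside it the mean is 2.64/0.833 = 3.2, so the relevant contrast is 6.8 vs 3.2. For ipilimumab it is 5.9 vs 2.6. ORR in the evaluable set is 0.359/(0.359 + 0.641 × 0.833) = 40.2%.

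**Worked case, 10% incidence, constant per-sample positivity p.** The chance of ever testing positive is the average of 1 − (1 − p)^k over the number of samples k. Solving for 10% overall gives p = 0.0227, so 14.5% of responders and 7.0% of non-responders are ever positive.

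- ORR in ADA-positive: 0.402 × 0.145/(0.402 × 0.145 + 0.598 × 0.070) = 58%.
- ORR in ADA-negative: 0.402 × 0.855/(0.402 × 0.855 + 0.598 × 0.930) = 38%.

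**Results for 5 to 20% incidence, no true ADA effect:**

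| Onset pattern | ORR, ADA-positive | ORR, ADA-negative |
|---|---|---|
| Constant per-sample positivity | 57–59% | 36–39% |
| Constant onset hazard, persistent ADA | 73–75% | 32–38% |
| All onset by Week 6 | about 42% | about 40% |

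**Sensitivity.** Suppose toxicity discontinuation runs at a rate reaching 18.1% at 6 months (timing assumed), and non-responders stay on treatment 1.5 months longer. Samples become 5.7 vs 3.5. At 10% incidence the difference is then 12.9 points (per-sample), 28.6 points (constant hazard) and 0 (by Week 6). Across these variants, with ipilimumab included and incidence from 3.2 to 40%, the ranges are 12–26, 28–45 and 0–3.5 points.

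**Week 6 landmark.** Everyone still on treatment at C2D1 has the same scheduled number of samples. In the base model all responders and 69% of non-responders remain, so ORR is 0.359/(0.359 + 0.641 × 0.69) ≈ 45% in both ADA groups, whatever the onset pattern.

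**AEs.** Longer exposure gives more samples and more AEs, which pushes towards a positive association. Toxicity that stops dosing also stops sampling, while Table 10.4.3-1 counts AEs for 100 days after the last dose. That pushes the other way.

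**The case against.** Nothing in the trial's decisions rests on this table. It is one exploratory item, described as a summary table or plot with no test attached, and the go criteria use PFS only. The same row already plans a table of ADA onset and duration, so late seroconversion would be visible. The SAP is still to be finalised before database lock and could add a rule. All of this stands and limits the weight of the point. It does not remove the bias, because the rule as written gives a skewed comparison under a heading that speaks of an effect.

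The size is also uncertain, and this stands too. The only ADA rate in the protocol is 2/63 = 3.2% for BMS-986207, with titers below 4 at one time point. Placebo samples are not analysed, so that drug concerns about 120 participants: 120 × 2/63 ≈ 4 positives. If 2 of 4 responded, the exact 95% interval would be 7 to 93%. No bias of the sizes above could be told from noise there.

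A reader might infer that a false association is certain to appear, or that ADA-positive participants will also show more AEs for the same reason. The protocol supports neither. The first depends on an onset pattern that it does not give, and for the second the direction is open.

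A reader might also conclude that the landmark should replace ever-positive status. It should not. Per 120 evaluable participants, the base model leaves about 5 (per-sample) or 2 (constant hazard) positives at a Week 6 landmark when incidence is 10%, and about 1.5 or 0.6 at 3.2%. It also excludes later seroconversion, which may matter for efficacy.

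**Conclusion.** The point holds for ORR. Ever-positive status combined with on-treatment sampling biases expected ORR upward in ADA-positive participants when ADA has no effect, and it could mask a real loss of efficacy. The size rests on the exponential time-on-treatment model and on assumed ADA rates and onset: about 20 points under constant per-sample positivity, 35 to 40 under a constant onset hazard, and 0 to 3.5 if onset is by Week 6. The first two shrink with toxicity discontinuation and treatment beyond progression. For BMS-986207 at its reported rate, chance would swamp the bias. For nivolumab and ipilimumab the protocol gives no rate. The AE comparison is confounded by time on treatment in an unknown direction. No primary or secondary conclusion is affected.

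**What to change.** In Table 10.4.4-1, or in the SAP before it is finalised:

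- Keep ever-positive status for incidence and for the planned descriptive table. Describe that table as an association, not an *effect*, and show the number of ADA samples and the time of onset by ADA group.
- Add a landmark comparison among participants still on treatment at C2D1 (Week 6). Take ADA status from the C1D22 and C2D1 samples for BMS-986207 and nivolumab, and from C2D1 alone for ipilimumab. Compare ORR, and AEs starting after the landmark, by that status.

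The first on-study scan is due at Week 6 (Table 2-2), so few responses should be documented before the landmark.

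The cost is wording and one extra table, with no new samples. The landmark comparison leaves out later seroconversions and participants off treatment before Week 6 (about 31% of non-responders in the model). It may contain few ADA-positive participants, so it should be reported descriptively.
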